#### **6.1.10.5 Withdrawal from the study (Early Termination)**

Volunteers may be withdrawn from the study permanently for the following reasons:

1. Volunteers may withdraw from the study at any time if they wish to do so, for any reason.
2. Following an adverse event at the discretion of the investigator (or designee).
3. Request of the primary care provider if s/he thinks the study is no longer in the best interest of the subject.
4. Subject judged by the investigator to be at significant risk of failing to comply with the protocol in a manner that might lead to harm to self or seriously interfere with the validity of the study results.
5. At the discretion of the FDA, Danish Health Authority, the PEI, the BfArm or investigator.

#### **6.1.10.6 Follow up after withdrawal from the study (Early Termination)**

Any adverse event resulting in withdrawal of a volunteer will be followed up until resolution or until the adverse event is judged by the principal investigator or designee to have stabilized where possible.

At the time of withdrawal, provided the volunteer is willing, all visit procedures from the final study visit will be performed as per the Time of Events Schedule (Appendix A).

The date and reason for withdrawal from the study (early termination) should be collected and reported to the Sponsor at the RU, the SMC and the local IRBs. Volunteers who are withdrawn from the study (early termination) after receiving at least one dose of 3BNC117 or romidepsin will not be replaced, but, wherever possible, will be followed until the time of their final planned visit.

A pregnant volunteer will not receive a 3BNC117 and/or romidepsin infusion. If pregnancy occurs after any 3BNC117 and/or romidepsin infusion, the participant will be asked to return for follow up every 4-6 weeks until delivery. Approximately 2-4 weeks after delivery, the baby will be examined by a pediatrician of the participant's choosing to assess the health status of the baby. Financial assistance will be provided to pay for the visit if necessary. The health status of the baby will be reported to the Sponsor at the RU, the SMC and the local IRBs.

## **6.2 Study Procedures**

### **6.2.1 Consent Procedure**

Prior to the initiation of any study related procedures, the potential subjects will be given a copy of the most recent IRB approved informed consent to read. Additionally, the PI or study staff member who has been designated to consent will discuss the specifics of the study including but not limited to the purpose of the research, procedures, time commitment, required tasks, test article or device, alternative treatments, benefits, risks, confidentiality etc. in a comprehensible (non-scientific) manner, using language readily understandable by the subject. Subjects will be told that participation is voluntary and that, if they do not consent, they will not be penalized. The person consenting will assure the voluntariness of the subject.

A private, confidential setting will be provided for the potential subject to read and discuss the informed consent free from coercion, undue influence or constraints of time. All subjects will be given a chance to ask questions and express concerns. They will be given the option to take the consent home and discuss it with family, friends, and /or health care providers. After a subject and the person conducting the consenting signs and dates the consent, the subject will be given a copy of the signed informed consent form.

An enrollment note will be written in the source document as to who obtained consent, how, when were questions asked and answered, and that a copy of the informed consent was given to the subject.

The "Teach Back" method will be used in the clinical research setting to ask research participants to repeat or "teach back" the information, concepts and directions that the staff member has attempted to convey to the subject. This method is used to assess

comprehension and retention of protocol requirements, adverse event information, risks and benefits, and the subject's rights described in the Informed Consent process.

Subjects for whom English, German or Danish is not a primary language will not be included in this study.

### **6.2.2 Study Assignment**

This is a randomized, open-label study. The study drugs are dispensed as specified by the randomization scheme generated by the Institute of Medical Statistics, Informatics and Epidemiology (IMSIE), University of Cologne. Participants are centrally assigned to a single treatment according to randomly permuted blocks of varying length. Randomization is stratified by study site and implemented as a 24-7 Internet service.

### **6.2.3 3BNC117 Administration Procedure**

3BNC117 will be provided in single-use vials containing 5 ml of the product at a concentration of 20 mg/ml. The site research pharmacist will calculate the volume of 3BNC117 to be administered. 3BNC117 will be administered as a slow intravenous infusion over 60 minutes in the site infusion unit. The calculated dose of 3BNC117 will be diluted in 0.9% Sodium Chloride, USP to a volume of 250 ml. 3BNC117 should be administered within 3 hours of preparation.

3BNC117 will be administered intravenously, via a peripheral vein in one of the upper extremities. The administration site should be free of potentially complicating dermatologic conditions. At the end of infusion, the IV line will be flushed with 20 ml of Normal Saline to ensure all the medication has been delivered.

Volunteers will remain in the infusion unit for 1 hour after drug infusion. If volunteers develop acute infusion reaction during 3BNC117 administration, the infusion will be held. Rescue medications, including acetaminophen, diphenhydramine and glucocorticoids will be available for use if clinically indicated. Infusion may be reinitiated after symptoms improve, and the remaining dose will be administered over 3 hours.

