### **7.3 Dispensing and Handling of the Investigational Products**

- 3BNC117 will be dispensed by the site research pharmacy. Trial personnel will ensure that the study ID number on the piggy-back matches the study ID assigned to the volunteer prior to administration.

3BNC117 will be provided in single-use vials containing 5 ml of 3BNC117 at a 20 mg/ml concentration. The appropriate dose will be calculated by the site research pharmacist according to subject's weight. 3BNC117 will be dispensed in a piggy-back, and diluted in normal saline (NaCl 0.9%), to a volume of 250 ml. It will be dispensed ready for administration by the study investigators and be good for infusion for 3 hours.

- Romidepsin will be dispensed by the site research pharmacy. Trial personnel will ensure that the study ID number on the piggy-back matches the study ID assigned to the volunteer prior to administration.

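### The 3BNC117 restart rule after an infusion reaction takes as long as the prepared product's whole use limit, so on a plain reading both cannot be met

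*Combined protocol and SAP*

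**What the plan says.** Two handling rules for 3BNC117 each appear twice in the protocol.

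- **Use limit.** Section 6.2.3 states: "3BNC117 should be administered within 3 hours of preparation". Section 7.3 says of the dispensed bag: "It will be dispensed ready for administration by the study investigators and be good for infusion for 3 hours". Section 7.3 does not say when its 3 hours begin.
- **Restart.** Section 6.2.3 states: "If volunteers develop acute infusion reaction during 3BNC117 administration, the infusion will be held". It continues: "Infusion may be reinitiated after symptoms improve, and the remaining dose will be administered over 3 hours". Section 6.1.5 gives the same restart rule.

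The planned administration is a single diluted dose ("The calculated dose of 3BNC117 will be diluted in 0.9% Sodium Chloride, USP to a volume of 250 ml") given in one hour ("3BNC117 will be administered as a slow intravenous infusion over 60 minutes in the site infusion unit").

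Three other provisions bear on the point. Section 6.1.10.1 ends the infusion outright for an immediate hypersensitivity reaction or a life-threatening event. Section 6.1.10.4 does not allow modification of the 3BNC117 dose. Section 6.1.5 leaves preparation to the site pharmacy's own procedures, which are not among the documents.

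**The concern.** The restart has the same length as the limit. Any time that passes between preparation and restart therefore carries the end of the infusion beyond the limit. The planned one-hour infusion has room to spare; the restarted one has none.

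The conflict arises at an awkward moment, when staff are caring for a participant who has just reacted. Section 12 names infusion and hypersensitivity reactions as the major safety concern with monoclonal antibodies in general. Staff would hold two written instructions that, read plainly, cannot both be followed, and the protocol does not say which gives way. Sites may resolve this differently: one may run the product past its stated limit, and another may leave part of the dose ungiven. If the dose given and the times are not recorded, antibody levels after such an infusion would be harder to interpret.

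**Working it through.** **Inputs from the protocol**

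- Use limit: 3 hours = 180 min from preparation (6.2.3); 3 hours with no stated clock start (7.3).
- Length of the restarted infusion: 3 hours = 180 min (6.1.5, 6.2.3).
- Planned infusion without a reaction: 60 min (6.2.3).

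**Inputs not in the protocol, so assumed**

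- p = minutes from preparation to first start.
- i = minutes infused before the hold.
- h = minutes of hold.

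**Step 1. Planned infusion.** It ends p + 60 min after preparation. It meets the limit when p ≤ 180 − 60 = 120 min, so the limit is workable when nothing goes wrong.

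**Step 2. Restarted infusion from the prepared product.** It ends at p + i + h + 180 min. The overrun is (p + i + h + 180) − 180 = p + i + h. An infusion that has begun and been held has i and h above zero, so the overrun is positive whatever the values.

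**Step 3. Range under assumed times**

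| p | i | h | End after preparation (min) | Overrun (min) |
|---|---|---|---|---|
| 0 | 1 | 0 (limiting case) | 181 | 1 |
| 0 | 10 | 15 | 205 | 25 |
| 30 | 10 | 30 | 250 | 70 |
| 60 | 30 | 30 | 300 | 120 |
| 120 | 59 | 60 | 419 | 239 |

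The rows show only how the sum behaves. They do not estimate what sites would see.

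**Step 4. Does a start-by reading remove the conflict?** If the limit governed only the start, and a restart counted as a start, the restart would have to begin by p + i + h ≤ 180 min. The first four rows meet this (1, 25, 70 and 120 min). The last does not (239 min). That reading would remove most of the conflict, but neither 6.2.3 nor 7.3 states it.

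**Step 5. Does a fresh preparation remove it?** With f minutes between the new preparation and its start, the infusion ends at f + 180 min, which is within 180 only if f = 0. A fresh bag would leave no slack, and no section provides for one.

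**The case against.** The best reply is that the text is looser than the arithmetic. The limit in 6.2.3 is worded as advice and could mean the time by which infusion must begin. Section 7.3 gives no clock start. Neither restart sentence says that the remainder must come from the same bag, so a fresh preparation is not forbidden. The site pharmacy procedures and the Investigator's Brochure may settle the matter, and neither is available here. All of this stands as a caution: the conflict is certain only on the plain reading. It does not resolve the point, because the protocol states none of these escapes and the fresh-bag route has no margin.

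The reply on scope is also sound. Section 6.1.10.1 removes the more serious reactions before the restart rule applies, and restarting is optional. Section 12 adds that such reactions are more common with antibodies containing murine elements than with human ones such as 3BNC117. Section 3.1.2.3 reports no serious or grade 3/4 events deemed related to 3BNC117.

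A reader might infer more: that Group A exposure would no longer be comparable across sites, or that the trial's results are at risk. The documents do not support that. Antibody levels and anti-drug antibodies are measured directly (6.2.12), their summaries are descriptive (6.2.13, 8.1), and no cross-site comparison of them is planned. Nor do the documents show that product used after the limit loses potency or does harm, since they give no stability figure for diluted 3BNC117 beyond the limit itself.

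**Conclusion.** The inconsistency is real. Read plainly, a restarted infusion of the prepared product ends p + i + h minutes past the use limit. That amount is always above zero, and the documents do not fix its size. The conclusion rests on taking the limit to cover the whole administration of the prepared product, which is what the wording of 6.2.3 says and what 7.3 fits.

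It affects only Group A infusions, planned as two per participant in an arm of 15, that are held for a reaction falling short of discontinuation under 6.1.10.1 and then restarted. The documents give no rate for such events. No effect on the primary endpoint, the sample size or any planned analysis is shown. It would be tempting to call this a design defect that must be fixed before the trial can be interpreted, but nothing in the documents carries it that far. It is a minor operational and safety inconsistency that is cheap to correct.

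**What to change.** The sponsor should reconcile the use limit (6.2.3, 7.3) with the restart rule (6.1.5, 6.2.3) against the existing stability data for the product. One consistent instruction should then stand in all three sections and in the site pharmacy procedure. It should say:

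- when the clock starts;
- whether the limit applies to the start or the end of infusion;
- what happens to the remainder when the limit would be reached.

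Which limit or infusion rate is right is for the sponsor to decide.

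The actual dose given and the end time of any held infusion should also be recorded. Section 9 lists infusion dates among the source documents but names neither of these items, although that list is not exhaustive.

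The cost is a few sentences in a short amendment, a matching edit to the pharmacy procedure, two items on the infusion record and, at most, a check of stability data already held.

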### **6.2.4 Romidepsin Administration Procedure**

Romidepsin is supplied as a kit containing 1 vial of romidepsin, 10 mg, and 1 vial of diluent for romidepsin, 2 mL, per carton. The volume of romidepsin to be administered will be calculated by the site research pharmacist, and diluted in 500 mL 0.9% Sodium Chloride, USP. Romidepsin is chemically stable for up to 8 hours at room temperature, upon reconstitution. When diluted in 500 mL 0.9% Sodium Chloride, USP, solution is stable for 24 hours. Romidepsin infusions will be administered over 120 minutes. Only staff trained to administer chemotherapeutic agents will administer romidepsin.

Romidepsin infusions will be administered by a trained research nurse with extensive experience with IV medication and the treatment of acute infusion-related reactions.

- Check electrolytes prior to infusion. Infusion will be administered if potassium, magnesium and calcium levels are within normal range. If potassium, magnesium and/or calcium level(s) are outside of the normal range, a repeat measurement will be obtained. If the electrolyte abnormality is confirmed, the infusion will be postponed. The participant will be supplemented as medically indicated and retested prior to infusion.
- Premedicate with ondansetron 8mg orally at least 30 min prior to infusion, to prevent nausea or vomiting
- Perform ECG 30 min after ondansetron, before infusion starts. The pre-infusion ECG will be read by a cardiologist. Infusion will be administered if QTc < 450 msec. (QTc measured from lead V3 or V4, using the Fridericia formula).
- Participants will be kept on continuous cardiac monitoring during infusion and a repeat ECG will be performed at 1 hour, during the infusion. If at 1 hour of infusion the QTc is > 450 msec or if it increases > 10 msec, hold infusion and consult with a cardiologist to determine appropriate monitoring and/or management, as clinically indicated;
- ECG will be repeated at the end of the infusion. If the QTc is > 450 msec or if it increases > 10 msec from the post-antiemetic ECG, repeat ECGs will be performed and vital signs measured at 2 and 4 hours post infusion and a cardiologist will be consulted to determine appropriate monitoring and/or management, as clinically indicated.
- Allergic reactions to romidepsin are uncommon but during the first 10 minutes of infusion all subjects will be under direct observation for acute allergic reactions.
- Vital signs (pulse, respiratory rate, blood pressure and temperature) will be monitored at the end of infusion, 30 (+/- 5) minutes, and 1 hour (+/- 5 min) post infusion.
- Subjects will be observed for adverse reactions at the study site for 1 hour after end of infusion.
- The study sites will have full and immediate access to handle and treat all acute medical emergencies including severe drug reactions.
- A medical doctor dedicated to the study will be present at all times at the study site during the infusions.
- A prescription for ondansetron will be given to participants to ameliorate any symptoms that may develop in the 48 hours following romidepsin infusion.

### 6.2.5 Medical History and Physical Examination

At the time of screening, a past medical history will be collected that will include details of any previous reaction to vaccination, and contraceptive practices. Interim medical histories will be collected at time-points according to the Time of Events Schedule (Appendix A).

A general physical examination will be conducted including weight, height, vital signs, and examination of skin, respiratory, cardiovascular, central nervous and abdominal systems. At the time of 3BNC117 and romidepsin infusions and at selected time-points thereafter, general and/or directed physical examinations will be performed according to

the Time of Events Schedule (Appendix A). A directed physical examination will include vital signs and any further examination indicated by history or observation.

### **6.2.6 Blood Collection and Shipment**

Venous blood will be collected at every study visit, usually from the antecubital fossa, according to the Time of Events Schedule (Appendix A). Total volume collected during the study will not exceed 550 ml in any 8-week period.

All specimens will be handled according to Processing Laboratory SOPs. Frozen PBMCs, plasma and serum will be processed and stored at the study sites.

### **6.2.7 Monitoring for cytokine release associated adverse events and treatment of cytokine release syndrome**

Based on previous clinical experience with similar monoclonal antibodies and with 3BNC117 (protocols MCA-835, MCA-866 and MCA-867), it is unlikely that administration of 3BNC117 will lead to cytokine release syndrome. However, a potential side effect of a monoclonal antibody can be the stimulation of a massive release of cellular cytokines, which can have profound effects on blood pressure, vascular integrity, and myocardial, lung, liver, and kidney functions. If cytokine release syndrome occurs, the volunteer may need to be treated with intravenous fluids, vasopressors, and high-dose corticosteroids and may require ventilatory support.

Study participants will be monitored for 1 hour post infusion in the site infusion unit. Access to a twenty-four hour on-call physician is available at all sites. The study sites are equipped with crash carts for immediate medical care. Supportive medications, including acetaminophen, diphenhydramine and glucocorticoids, will be available at both clinical sites for use if clinically indicated. In case of an emergency, after stabilization of the volunteer, he/she will be transferred to a tertiary care center for specialized medical care.

### **6.2.8 Family Planning Counseling**

During screening and subsequent study visits, study personnel will counsel volunteers about the importance of prevention of pregnancies and the use of condoms, as well as other effective family planning methods. Condoms will be provided.

Participants will be required to use 2 effective forms of contraception (i.e. condom with spermicide, diaphragm with spermicide, progestin-only containing intrauterine device (IUD) (eg, Mirena, Implanon, Nuva Ring), non-estrogen containing formulations of hormonal birth control drugs with condom) for the study duration.

Pregnancy tests will be conducted at each clinic visit as outlined in the Time of Events Schedule (Appendix A). Should pregnancy be detected before administration of 3BNC117 or romidepsin, the volunteer will not receive the infusion. Should pregnancy be detected after any 3BNC117 or romidepsin infusion, a pregnant volunteer will be asked to return for follow up every 4-6 weeks until delivery. Should pregnancy occur, ART will not be discontinued or will be resumed as soon as the study investigators become aware of the pregnancy. Approximately 2-4 weeks after delivery, the baby will

be examined by a pediatrician of the participant's choosing to assess the health status of the baby. Financial assistance will be provided to pay for the visit if necessary. The outcome of the pregnancy and the health status of the baby will be reported to the Sponsor at the RU, the local IRBs, and the SMC.

## **6.2.9 Compensation**

Study volunteers will be compensated according to local standards.

## **6.2.10 Safety Assessments**

### **6.2.10.1 Solicited Adverse Events**

Solicited adverse events in this study include presence of feverishness, chills, headache, nausea, vomiting, diarrhea, malaise, myalgia and arthralgia, as well as ocular complaints such as conjunctival erythema, excessive tearing or burning within 2 weeks of 3BNC117 and/or romidepsin administration, and will be collected prospectively by structured interviews on the 3BNC117 and romidepsin infusion and post-infusion follow up visits; recorded and graded according to pre-established criteria (see C). The CTCAE v4.03 grading scale will be used to grade infusion-related adverse events. The DAIDS Table for Grading the Severity of Adult and Pediatric Adverse Events, Version 2.0 will be used to grade all non-infusion-related adverse events.

Vital signs (pulse, respiratory rate, blood pressure and temperature) will be measured prior to 3BNC117 or romidepsin administration, at the end of infusion, at 30 minutes, and 1 hour after the infusion is completed, graded according to Appendix C and recorded. Similarly, the occurrence of adverse events will be assessed and graded. All medications required for treatment of adverse events will be recorded.

### **6.2.10.2 Other Adverse Events**

Other adverse events will be recorded following an open question to volunteers, with the dates of commencement and resolution and any medication required. All adverse events will be followed to resolution. Serious adverse events will be collected during the entire study period. They will be graded as indicated in Appendix C.

Safety monitoring at each clinical site will be conducted by an external monitor and by an external Study Monitoring Committee (SMC). The RUH, AUH and UCH IRBs will conduct the initial review of the proposed study and will follow progress through annual reports and by immediate notification of serious and unanticipated adverse events. Any serious adverse events will be reviewed by the study investigators immediately. Site investigators will notify the local IRB and the sponsor at the Rockefeller University within 2 working days from the investigators being made aware of the event. The RU sponsor will notify the FDA, Danish Health Authority, PEI, and BfArm per 21 CFR 312 (Appendix G). The SMC will be available to the investigators for consultation and review of severe adverse events if needed.

